2. LAY SUMMARY

High blood pressure (BP) (hypertension) during and following pregnancy affects around 80,000 women* each year in the UK, and can lead to very serious problems such as pre-eclampsia or stroke. In the longer term, women who had high BP in pregnancy have an increased risk of heart attack and stroke, and this seems to be linked to their blood pressure in the early weeks following birth.

After birth, women's BP can remain elevated, but in most cases it returns to normal over 2–12 weeks. During this period, blood pressure medication needs to be adjusted to achieve the correct control. Our previous research suggests that better BP control during this period is associated with improved long-term health outcomes. This trial aims to test whether women with high BP, can achieve lower blood pressure than is usual in the weeks and months following birth, through self-monitoring and adjusting their own medication.

Women recruited to the study will be randomly assigned to one of two groups: either monitoring their own blood pressure and using this to manage their blood pressure medication, or receiving the standard care that they would otherwise have. Participants allocated to 'usual care' will have their BP monitored and medication adjusted by their obstetrician, GP and midwife as normal. Participants allocated to the 'self-management' group will use a home BP monitor daily following discharge from hospital after birth until their blood pressure has settled, and then once a week. They will be provided with an individualised schedule (via a specially designed app) for gradually adjusting their medication(s) in line with their BP readings, overseen by their obstetrician, GP and midwife.

Women will be followed up for 12 months, and the trial will measure blood pressure as well as their experiences and costs. Results will be widely shared in both professional and lay media.

*Throughout the Protocol, in our references to women, we also encompass birthing people within this context

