9.4. Baseline Assessment

The baseline visit will take place as soon as is practical (within 7 days) in hospital after delivery or remotely/at home for women who have left hospital already and will last approximately 45 minutes. For eligible participants who have already consented before the baseline assessment (e.g. if they have been in hospital for a few days and consented before birth), consent will be re-checked to ensure that participants are still happy to continue on the trial, and this will be documented in the participant's maternity notes and on the study CRF. For those not previously consented, the consent process described above will take place before any further activity. Inclusive recruitment procedures will be used.

Any data not already collected as per eligibility screening in 9.2 above will be collected.

Baseline BP will be collected the last 3 postnatal BP readings within 24 hours of randomisation (up to 3 if less than 3 available in records)

We will measure (or ask for self-measurement of) a participant's left upper arm (or right arm if left arm cannot be used for blood pressure monitoring) in order to guide choice of blood pressure cuff size.

It is at this visit that participants will be randomised. If they are randomised to the intervention arm, they will be provided with a blood pressure self-monitor, and taught to use it. For participants in the usual care arm, they will be given a bag to put their monitor in that indicates it should only be used for taking readings at follow up time points (if follow ups are remote). Prior to discharge from hospital, participants in the intervention group will receive the intervention as per section 9.6 below.

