9.6. Description of study intervention(s), comparators and study procedures (clinical)

9.6.1 Description of study intervention: Self-management of blood pressure

Women randomised to self-management of blood pressure will have an individualised medication adjustment schedule (based on NICE guidance for medication adjustment postpartum) (NICE, 2019), (Webster K, 2019). They will be provided with, and taught how to use, a validated home blood pressure monitor, and perform daily blood pressure readings until their blood pressure has settled on treatment or they have discontinued treatment. Readings will transmitted to their health professionals (obstetricians for first 2 weeks then GP) via a bespoke app (My Blood Pressure Care) (see 5.3 above.

The blood pressure monitor used will be Microlife WatchBP® Home as these have been validated for use in pregnancy and pre-eclampsia. Women will be provided with written instructions regarding use of the monitor. When antihypertensive treatment is discontinued or blood pressure is stable on treatment (in each case for a 7 day period), we will ask them to continue weekly blood pressure measurements until the primary outcome measurement at six months. Should blood pressure increase again during the weekly measurement period, the clinician will advise a change back to daily measurement via the app. Clinicians will have access to the self-monitoring BP data in order to advise on medication titration. Women and clinicians will both receive prompts for action in the event of raised or low blood pressure readings.

Participants in the intervention arm will be asked to perform daily BP readings at the same time each morning, at a time that is convenient to them: After 5 minutes rest they will perform two readings, more than 1 minute apart, and the second reading acted upon, in terms of how to adjust their medication. The self-monitoring BP data will be communicated centrally to their usual care team through the use of a smart phone app. This service will respond to participants regarding the level of their BP and what action is required (if any). Participants in this group will be provided with an individualised medication adjustment schedule via the app based on:

- Current treatment (which drugs, what doses)
- NICE guidance for management of hypertension in pregnancy (NICE, 2019) suggests the following categories
 - o If < 130/80 mmHg reduce / stop treatment
 - o If < 140/90 mmHg consider reducing / stopping treatment

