 - o If \geq 150/100 mmHg increase / start treatment
 - o If ≥ 160/110 mmHg requires hospital review

The individualised medication adjustment schedules for each participant will be created by the participant's usual care team in conjunction with the research team.

Participants will be provided with a Freephone telephone number to contact for any trial-related queries.

Participants in the intervention arm will be advised to attend their local maternity unit for urgent review if blood pressure is $\geq 160/110$ mmHg or they develop symptoms which may be associated with hypertension (headache, visual disturbance, vomiting or upper abdominal pain). They will also be given instructions on contacting their GP or midwife should their blood pressure be greater than 150/100 mmHg, or less than 100 systolic (or sustained $\geq 140/90$ mmHg). Other messaging will relate to the level of blood pressure recorded (see NICE blood pressure categories above) and participants will receive simple advice regarding appropriate actions. If there is no evidence that the participant has made contact with a clinician/GP within a week after a BP reading requiring review was entered, the participant's GP will be sent a letter informing them of this.

In addition, participants randomised to the intervention will receive usual postnatal care provided by a combination of obstetrician, community midwife, health visitor and GP including routine visits and examinations. Participants randomised to the intervention will be provided with a letter to share with their community midwife/ maternity support worker, informing the teams providing postnatal care of the woman's participation in the trial.

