10.4. Expected Serious Adverse Events

The following SAEs (which must also fulfil at least one of the criteria listed in section 10.1) may be expected to occur in this population, as they relate to the disorder being investigated (pregnancy and associated hypertensive diseases). These will be collected as outcomes and do not need to be reported as SAEs.

Potentially related to BP management	Unrelated to BP management
BP ≥ 160/110 mmHg	Vaginal bleeding
BP < 90/50 mmHg whilst on treatment	Endometritis
	Sepsis
Faint	Pyelonephritis
Fall	Mastitis
Headache	Surgical site infection
Vomiting	Paralytic ileus
Upper abdominal pain	Visceral injury (ureter, bladder, bowel)
	Pelvic collection
	Haematoma

Regardless of whether they might be expected in this population, the following serious adverse events will be reported as SAEs:

- Stroke
- Intracranial haemorrhage
- Seizure

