11.1.1 Description of the Statistical Methods

All analyses will be conducted in accordance with Oxford Primary Care CTU SOPs.

Internal pilot: Descriptive statistics will be used to describe recruitment of the first 100 participants (section 9.12).

In accordance with CONSORT guidelines, we will record and report participant flow. Descriptive statistics of recruitment, drop-out/withdrawal and completeness of intervention will be reported.

Baseline variables will be presented by randomised group using frequencies (with percentages) for binary and categorical variables and means (standard deviations) or medians (with lower and upper quartiles) for continuous variables. There will be no tests of statistical significance nor confidence intervals for differences between groups on any baseline variables.

The primary estimand is the mean difference in daytime ambulatory diastolic BP at 22-39 weeks for all randomised participants, as defined by protocol eligibility criteria, regardless of what intervention they actually received or adherence of intervention. A generalised linear mixed-effects model utilising data collected all time-points from randomisation will be fitted to the data with mean daytime diastolic BP measured at 22-39 weeks as the response variable, adjusting for minimisation factors for principal diagnosis (chronic hypertension or gestational hypertension/pre-eclampsia), mean postnatal diastolic blood pressure (last 3 readings in clinical record) ($<83/\ge83$), number of anti-hypertensive medications ($<2/\ge2$) and randomised group fitted as fixed effects and the model will include site as a random effect. An adjusted mean difference at 22-39 weeks between the randomised groups, together with a 95% confidence interval and a P value, will be estimated from the model.

A similar approach will be used for continuous secondary outcomes, and generalised linear model for binary outcomes. Time effects will be included in the model for repeated measures outcomes where appropriate.

Safety outcomes will be compared using Fisher's exact or Chi-square test.

Pre-specified subgroup analyses of the primary outcome will be explored by baseline diastolic BP, principal diagnosis, ethnicity, indices of multiple deprivation quintiles, social status, and parity.

Standard residual diagnostics will be assessed for the appropriateness of the model.

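### BP-threshold events are detected unequally by arm, so a raw between-arm safety test would mix blood pressure control with how often BP is measured

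*Protocol*

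**What the plan says.** **The events.** Protocol section 10.4 gives a table of serious events expected in this population. The column for events potentially related to BP management includes BP ≥160/110 mmHg and BP <90/50 mmHg while on treatment. Of the listed events it says "These will be collected as outcomes and do not need to be reported as SAEs". The same paragraph limits the list to events "which must also fulfil at least one of the criteria listed in section 10.1".

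**The test.** Section 11.1.1 says "Safety outcomes will be compared using Fisher's exact or Chi-square test". It makes no allowance for the number or source of BP readings.

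**Measurement in the self-management arm.** Section 9.6.1 asks these women to "perform daily blood pressure readings until their blood pressure has settled on treatment or they have discontinued treatment". After seven days stable on treatment, or off it, "we will ask them to continue weekly blood pressure measurements until the primary outcome measurement at six months". At ≥160/110 mmHg, or with relevant symptoms, they "will be advised to attend their local maternity unit for urgent review". Usual care continues alongside.

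**Measurement in the usual-care arm.** Section 9.4 gives these women the same monitor in a bag indicating that "it should only be used for taking readings at follow up time points" where follow-up is remote. Other readings come from usual postnatal care. Section 5.4 describes that as checks on at least alternate days for the first 14 days after birth.

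**The window.** Section 10.2 runs safety reporting from baseline to the 22-39 week visit.

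**The concern.** An event defined by a BP threshold can be recorded only if someone measures BP. One arm measures far more often, and is directed to a maternity unit when a reading is high. The number of women with such an event therefore depends on two things: what the intervention does to blood pressure, and how often anyone looks. Fisher's exact or chi-square on raw counts cannot separate them.

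At stake is the reading of the safety results. Self-management could appear to cause severe hypertension when BP is the same in both arms, or a true reduction could be masked. Section 9.8 already guards against a similar bias: it takes up to six readings at visits because women who self-monitor may become more habituated to measurement. Nothing comparable protects the threshold events.

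**Working it through.** The protocol states no rate for these events, so there is no figure of its own to reproduce. The check counts measurement occasions, then asks what unequal counts do when true BP is equal.

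**1. Occasions to week 26**
- Length of the daily phase: not fixed. The lay summary says of raised BP after birth that "in most cases it returns to normal over 2–12 weeks", so 14 to 84 days is used.
- Self-management home readings: 14 daily + 24 weekly = 38, up to 84 daily + 14 weekly = 98.
- Usual checks in both arms: about 7 alternate-day checks in the first 14 days + 3 trial visits = 10, or 14 if four further contacts are assumed.
- Ratio, lowest: (38 + 14)/14 = 3.7. Ratio, highest: (98 + 10)/10 = 10.8.

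**2. Women with at least one reading ≥160 systolic or ≥110 diastolic, equal true BP**

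This was simulated, because readings within a woman are correlated and BP falls after birth. None of the following assumptions comes from the protocol:
- mean BP falls from 138/87 to 122/79 mmHg with a 25-day time constant;
- between-woman SD 12/8 mmHg; within-woman SD 8/5 to 10/7 mmHg;
- daily phase of 21, 42 or 84 days, then weekly, with full adherence;
- in both arms, alternate-day checks from day 4 to day 14, three visits, and 0 or 4 further contacts.

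| | Usual care | Self-management | Ratio |
|---|---|---|---|
| Whole window | 11% to 18% | 19% to 33% | 1.7 to 1.9 |

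The ratio is much smaller than the ratio of occasions for two reasons. The early checks, when BP is highest, are shared by both arms, and repeat readings in one woman tend to find the same women.

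**3. Effect of the seriousness criterion**

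Let R be the ratio in step 2 and f the share of serious events that would surface without any home reading. If a detected crossing is equally likely to meet a section 10.1 criterion in either arm, the ratio of serious events is f + (1 − f)R.

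| f | R = 1.7 | R = 1.9 |
|---|---|---|
| 0 | 1.70 | 1.90 |
| 0.5 | 0.5 + 0.5 × 1.7 = 1.35 | 0.5 + 0.5 × 1.9 = 1.45 |
| 0.9 | 0.9 + 0.1 × 1.7 = 1.07 | 0.9 + 0.1 × 1.9 = 1.09 |
| 1 | 1.00 | 1.00 |

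The protocol gives nothing from which to estimate f.

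**4. What such ratios do to the test**

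The planned total of about 690, allocated 1:1, gives 690/2 = 345 per arm. Fisher's exact test at two-sided 5%, with no true difference in BP, rejects as follows for two assumed usual-care event rates:

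| Detection-driven ratio | Usual-care rate 5% | Usual-care rate 10% |
|---|---|---|
| 1.0 | 3% | 4% |
| 1.1 | 4% | 6% |
| 1.5 | 22% | 47% |

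If most serious events surface anyway, the distortion is negligible. If about half or more depend on home readings, it is not.

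**The case against.** **The seriousness criterion.** A home reading over the threshold is not an event in itself under section 10.4, and urgent review is not inpatient admission. This stands, and it is why no fixed size can be given. It does not remove the problem. Only self-management women are sent by the trial for review on a home reading, which can lead to an admission. Section 10.1 also admits important medical events on clinical judgement, so a detected reading can qualify without admission.

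**The comparison is inferred.** Section 11.1.1 does not define safety outcomes, the outcome tables do not list the threshold events, and the SAP, which is not shown, may settle the matter. This also stands. The natural reading is nonetheless that events called outcomes in the safety section fall under the safety test. If that is not intended, one sentence would say so.

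**Real consequences.** An admission prompted by self-monitoring is a true effect of the intervention. All-cause and pregnancy-hypertension admissions are already secondary outcomes taken from records review. This is correct, and that comparison is not challenged. The point here concerns only events defined by a BP reading.

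**A stronger reading.** From the 4- to 11-fold difference in occasions, a reader might infer several-fold more events under self-management. The documents do not support that. It would require every crossing reading to count, readings to be independent, and the risk per reading to stay constant. Section 10.4 rules out the first. Repeated readings in the same woman make the second implausible, and the lay summary's account of BP settling speaks against the third. Nor does the claim extend to <90/50: it applies only on treatment, so readings after stopping cannot produce it.

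**Conclusion.** The point holds in a limited form. Ascertainment of BP-threshold events is unequal by design, and an unadjusted between-arm test of them would mix BP control with measurement intensity. For ≥160/110 the detection ratio under equal true BP is about 1.7 to 1.9 over the whole window before the seriousness criterion. After it, the ratio lies between 1.0 and that figure, with nothing in the protocol to place it more closely.

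These figures rest on the assumed BP course, variances, adherence and visit counts given above. The <90/50 threshold was not quantified. That these events enter the section 11.1.1 test is the natural reading, not an explicit statement. The weakness affects interpretation of safety, not the primary ambulatory outcome.

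**What to change.** In sections 10.4 and 11.1.1:

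- Record for each BP-threshold event how it was first detected: home or app reading, usual-care contact, or scheduled trial visit.
- Make the formal between-arm comparison of threshold crossings on readings taken on the schedule common to both arms within the safety window, that is the 6, 12 and 22-39 week visits. The 48-60 week visit lies outside that window. Ambulatory monitoring is a poor basis, since section 11.2 reports completion below 50%.
- Report all BP-threshold events that meet a section 10.1 criterion, including those between visits, descriptively by arm and source of detection. State the ascertainment caveat and do not apply a raw significance test.
- Keep formal safety tests for events that do not depend on how often BP is measured, such as stroke, intracranial haemorrhage and seizure.

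The cost is wording in two sections and a new source field, since the protocol does not show that the source of each reading is recorded. Fewer threshold events would enter the formal test; the descriptive report keeps the serious between-visit events in view.

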11. STATISTICS AND ANALYSIS

11.1. Statistical Analysis Plan (SAP)

The statistical aspects of the study are summarised here. A detailed statistical analysis plan will be developed prior to randomisation of the first participant with prespecified sensitivity and subgroup analysis.

11.1.1 Description of the Statistical Methods

All analyses will be conducted in accordance with Oxford Primary Care CTU SOPs.

Internal pilot: Descriptive statistics will be used to describe recruitment of the first 100 participants (section 9.12).

In accordance with CONSORT guidelines, we will record and report participant flow. Descriptive statistics of recruitment, drop-out/withdrawal and completeness of intervention will be reported.

Baseline variables will be presented by randomised group using frequencies (with percentages) for binary and categorical variables and means (standard deviations) or medians (with lower and upper quartiles) for continuous variables. There will be no tests of statistical significance nor confidence intervals for differences between groups on any baseline variables.

The primary estimand is the mean difference in daytime ambulatory diastolic BP at 22-39 weeks for all randomised participants, as defined by protocol eligibility criteria, regardless of what intervention they actually received or adherence of intervention. A generalised linear mixed-effects model utilising data collected all time-points from randomisation will be fitted to the data with mean daytime diastolic BP measured at 22-39 weeks as the response variable, adjusting for minimisation factors for principal diagnosis (chronic hypertension or gestational hypertension/pre-eclampsia), mean postnatal diastolic blood pressure (last 3 readings in clinical record) ($<83/\ge83$), number of anti-hypertensive medications ($<2/\ge2$) and randomised group fitted as fixed effects and the model will include site as a random effect. An adjusted mean difference at 22-39 weeks between the randomised groups, together with a 95% confidence interval and a P value, will be estimated from the model.

A similar approach will be used for continuous secondary outcomes, and generalised linear model for binary outcomes. Time effects will be included in the model for repeated measures outcomes where appropriate.

Safety outcomes will be compared using Fisher's exact or Chi-square test.

Pre-specified subgroup analyses of the primary outcome will be explored by baseline diastolic BP, principal diagnosis, ethnicity, indices of multiple deprivation quintiles, social status, and parity.

Standard residual diagnostics will be assessed for the appropriateness of the model.

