We will ask women whether or not they are involved in any other relevant clinical research projects. Involvement in other research projects does not exclude women from this trial unless they are directly involved with a trial that might affect their anti –hypertensive prescription.

Personal data as follows will be collected and stored separately from the clinical database. This is to facilitate contact with participants during the study, and to arrange home follow-up visits (if participants agree):

- Forename and surname
- Address including full postcode
- NHS Number (to allow access to participant's medical records)
- Telephone number (mobile)
- Email address

Details of the following aspects of the diagnosis of pregnancy hypertension and its complications will be taken from the medical records either pre or post natally but before randomisation and recorded:

Blood pressure (BP) at booking

- Diagnosis of chronic or gestational hypertension
- Separate diagnosis of pre-eclampsia (including proteinuria or other maternal dysfunction)[can follow chronic or gestational or be denovo)
- Multiple pregnancy
- Maternal complications (renal dysfunction, HELLP/ELLP syndrome, eclampsia, placental abruption)
- Fetal Death

Details of postnatal hypertension

- Date of delivery and estimated date of delivery (to calculate gestation at delivery)
- Baseline postnatal anti-hypertensive drugs used
- Baseline blood pressure: last 3 postnatal readings within 24 hours of randomisation

Participants will be asked to complete the EQ-5D-5L health-related quality of life questionnaire and the Short Form Anxiety Inventory Questionnaire at this visit.

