9.7. Randomisation

Participants will be randomised by the site study team after the baseline visit and before primary hospital discharge, using a secure web-based randomisation system provided by the Oxford Primary Care Clinical Trials Unit. If a participant has been discharged from hospital before being randomised the research midwife will contact the participant and carry out remote consent and randomisation over the phone within 7 days of being discharged. The system will allow for the allocation of participants to the two

randomisation groups: usual care or self-management on a 1:1 basis and for this allocation to be stratified according to recruitment site with minimisation for principal diagnosis (chronic hypertension or gestational hypertension/pre-eclampsia), and mean postnatal diastolic blood pressure (last 3 readings in clinical record, <83mmHg vs \geq 83mmHg), and number of antihypertensive medications (<2 vs \geq 2 medications).

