11.2. Sample Size Determination

Using data from the SNAP-HT feasibility trial and its follow-up study (Cairns AE, 2017), it is estimated that the standard deviation of mean daytime ambulatory diastolic BP at 6 months will be 10mmHg (inflated from 8mmHg to take into account greater heterogeneity between recruiting sites in this multicentre trial); 314 women (157 per group) are needed to detect ≥4mmHg difference (standardised difference 0.4) with alpha 0.05 and 90% power, and 15% post-randomisation drop out.

The aim will be to recruit approximately similar numbers of women with gestational hypertension/pre-eclampsia and chronic hypertension meaning that 628 women will be included overall. Assuming that the heterogeneity between these groups is small enough, 80% power will be retained for at least 5mmHg difference in diastolic BP for sub-groups of at least 40% of the total sample size, e.g. white vs non-white (expected 60:40 proportions). Furthermore, if appropriate to combine, the full sample of 628 women would allow smaller effect sizes to be detected (effect size = 0.22 - 80% power, effect size = 0.26 - 90% power).

During the regular monitoring of the trial, the TMG noted a higher proportion of gestational hypertensive women were enrolled in the study, (approximately 80%). In addition, the monitoring of ABPM completion showed low completion rates of ABPM (<50%). The sample size was subsequently inflated for operational reasons to retain the pre-specified power in the original sample size calculation in both gestational and chronic hypertensives as far as possible. Therefore, the sample size was updated to ensure 532 (266/0.5) gestational hypertensive women would be randomised and the remaining chronic hypertensive women to be recruited as far as possible in the recruitment period. Thus the recruitment period will allow approximately a total of 690 women.

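### The primary model adjusts for baseline diastolic BP only as below versus at or above 83 mmHg, although the readings are collected as values; a continuous term would give a modest gain in precision

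*Protocol*

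**What the plan says.** Section 11.1.1 (Description of the Statistical Methods) builds the primary model on the allocation factors: "adjusting for minimisation factors for principal diagnosis (chronic hypertension or gestational hypertension/pre-eclampsia"), followed by "mean postnatal diastolic blood pressure (last 3 readings in clinical record"), split at below 83 mmHg versus 83 mmHg or more, then number of antihypertensive drugs and randomised group as fixed effects, with site as a random effect. The coding of baseline diastolic BP is therefore stated in the protocol and is not left open.

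Section 9.7 (Randomisation) uses the same cut for the minimisation: "last 3 readings in clinical record, <83mmHg vs" 83 mmHg or more.

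The underlying readings are recorded. The screening section (9.2) lists "Baseline blood pressure: last 3 postnatal readings within 24 hours of randomisation", and section 9.4 allows for women with fewer: "up to 3 if less than 3 available in records". Nowhere does the protocol enter the continuous mean in the primary model.

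Section 11.1.1 also extends a similar approach to the continuous secondary outcomes, which include systolic BP, without saying which baseline term they use.

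**The concern.** Minimisation needs categories; an analysis model does not. Taking the minimisation cut into the model treats a woman at 84 mmHg and one at 100 mmHg as the same, although the database can tell them apart. Whatever baseline diastolic BP predicts about the later ambulatory value within each category is left in the residual variance.

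The stake is precision on the primary outcome, in a trial where section 11.2 reports that fewer than half of the ambulatory recordings were being completed and where recruitment was enlarged to protect power. A secondary point is that minimisation balances the two categories among all women randomised. It does not balance the BP distribution within a category among those who complete the ambulatory measurement.

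**Working it through.** **Inputs from the protocol.** Section 11.2 states that the "standard deviation of mean daytime ambulatory diastolic BP at 6 months will be 10mmHg", with a difference of 4 mmHg, 90% power, alpha 0.05 and 15% drop-out. Section 11.6 makes the test two-sided, and section 9.7 gives 1:1 allocation.

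**Input that the protocol does not give.** It gives neither the correlation r between baseline mean diastolic BP and the ambulatory outcome nor the baseline distribution. I assume r = 0.2 to 0.5, normality and a linear effect.

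**Step 1: the plan's own figure.** A two-sample t-test with a standardised difference of 4/10 = 0.4 needs 133 per arm (power 0.901), that is 266 evaluable. 133/0.85 = 156.5, rounded up to 157 per arm or 314 in total, as stated. 266/0.5 = 532 gives the revised target for gestational hypertension. The calculation takes no credit for covariate adjustment.

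**Step 2: loss from the cut.** For a normal covariate cut at quantile q, the share of its explained variance that is kept is φ(z_q)² / [q(1−q)], where φ is the standard normal density. At the median this is 2/π = 0.637, a loss of 36.3%. A simulation with r = 0.4 gave 36.5%. Off the median the loss grows:

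| Split | Loss |
|---|---|
| 50/50 | 36.3% |
| 40/60 | 37.8% |
| 30/70 | 42.4% |
| 25/75 | 46.1% |
| 20/80 | 51.0% |

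**Step 3: effect on the treatment comparison, cut at the median.** Relative residual variance is 1 − r² with the continuous term and 1 − (2/π)r² with the binary term. Their ratio is the inflation of the treatment-effect variance. Example for r = 0.3: (1 − 0.637 × 0.09)/(1 − 0.09) = 0.9427/0.91 = 1.036. The adjusted SD is 10 times the square root of the residual variance. Power (normal approximation) is for 4 mmHg with 133 evaluable per arm.

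| r | Variance inflation | Power, binary | Power, continuous | n per arm for 90%, binary | n per arm for 90%, continuous |
|---|---|---|---|---|---|
| 0.2 | 1.5% | 91.1% | 91.5% | 128 | 127 |
| 0.3 | 3.6% | 91.9% | 92.8% | 124 | 120 |
| 0.4 | 6.9% | 93.1% | 94.5% | 118 | 111 |
| 0.5 | 12.1% | 94.5% | 96.5% | 111 | 99 |

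With no covariate, the same approximation gives 90.4% power at 133 per arm and needs 132 per arm for 90%.

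**Step 4: a larger evaluable number.** If half of 690 women were evaluable (345, an upper figure because completion is below 50%), the same formula gives 96.4% versus 96.7% at r = 0.2 and 98.2% versus 99.0% at r = 0.5. That is a gain of about 0.2 to 0.8 points. The confidence interval would be about 1% to 6% narrower.

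**The case against.** The strongest reply is that nothing here is wrong. Sections 9.7 and 11.1.1 agree, the model adjusts for the factors used in the allocation, the estimate is unbiased, and the sample size counted on no gain from covariates, so no promised power is lost. All of that stands. A reader might infer from the word dichotomised that the primary result is biased or its type I error inflated; the documents do not support that.

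A reader might also take the 36% as a share of the trial's information. It is a share of what one covariate explains. At r = 0.3 the covariate explains 9% of the outcome variance, and 36% of that is about 3%.

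The covariate may also be weak. Baseline is one to three chart readings around randomisation, in women on treatment within about a week of birth. The outcome comes at 22 to 39 weeks, and section 5.2 reports that more than 95% were off medication at six months in the feasibility trial. The low end of the assumed range may therefore be nearer the truth. Diagnosis, number of drugs and site may already carry part of the same information, which Step 3 ignores.

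The argument about selected completers is partly met: section 11.7 adds predictors of missingness as fixed effects and plans multiple imputation and pattern-mixture analyses. One might extend the point to the baseline-BP subgroup analysis and the imputation model, but the protocol does not state how baseline BP is coded in either. Those belong to the SAP.

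Finally, a single linear term does not reproduce a step at 83 mmHg and adds a linearity assumption. That is fair, and it shapes the fix.

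**Conclusion.** The point holds as one of efficiency. The protocol fixes a two-level coding where the measured values are available, and this forgoes some precision on the primary outcome. The loss is about 36% of the variance that baseline diastolic BP explains, under normality, linearity and a cut at the median, and more if the cut is off-centre. In terms of the treatment effect, its variance is 1.5% to 12.1% higher for r between 0.2 and 0.5: about 0.4 to 2 points of power, or 1 to 12 women per arm, at the planned 133 evaluable per arm. The coding is certain from the text. The size is conditional, because neither r nor the baseline distribution is in the protocol. It is a modest improvement worth making because it costs almost nothing, and the planned analysis remains valid without it.

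**What to change.** In section 11.1.1 and the SAP, replace the two-level term in the primary model with the mean of the available baseline diastolic readings (one to three) as a continuous covariate. Prespecify it as linear, or as a spline if the relation is not linear. The binary factor may be kept beside it so that the allocation factor stays visibly in the model. Leave the 83 mmHg cut in section 9.7 for the minimisation, and leave the other factors and site as they are.

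Where the similar approach is applied to systolic outcomes, adjust for the continuous baseline systolic BP, which section 6 lists as a baseline measure.

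The cost is a line in the SAP and a matching edit to the protocol, with no new data and no change for sites. Section 11.8 has the final SAP agreed before data lock and before any analysis, so the change can still be prespecified. The one drawback is the linearity assumption, which the spline handles.
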